9.3.2.5 Treatment exposure and compliance

The following will be derived from data collected in the Study Drug Accountability form of the eCRF:

For each visit post baseline:

- Number of tablets taken = Number of tablets dispensed at previous visit – Number of tablets returned for the visit
- Duration = (date of last dose) – (date of first dose) + 1.
- Tablets Prescribed = Duration x 2
- Study drug compliance (%) = $100 \times (\text{Number of tablets taken}) / (\text{Number of tablets prescribed})$

For the whole study:

- Treatment Duration = (Date of last dose) – (Date of first dose) + 1
- Cumulative dose is the total number of tablets taken across all study days times 15 mg
- Average daily dose is the cumulative dose divided by the total treatment duration
- Total number of tablets taken = Sum of numbers of tablets taken over all visits
- Total number of tablets prescribed = Sum of tablets prescribed over all visits
- Overall study drug compliance (%) = $100 \times (\text{Total number of tablets taken}) / (\text{Total number of tablets prescribed})$

If “Number of tablets returned” is missing, the Number of tablets returned will be assumed to be 0 in the calculations of treatment exposure and compliance but will be presented as missing in the listings.

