9.3.4 Safety derivations

9.3.4.1 Adverse events

Adverse events (AEs) and serious adverse events (SAEs) will be collected from the time of signature of the informed consent form (ICF), until after either the 7-Day follow-up period is completed or up to 30 days after the patient has stopped study treatment, whichever is later.

All AEs and SAEs are recorded in the Adverse Event Form.

A treatment-emergent AE (TEAE) is defined as an AE that meets any of the following conditions:

- begins on or after the first dose of study drug and on or before the stop of study drug + 35 days
- begins before the first dose of study drug and worsens on or after the first dose of study drug and on or before the stop of study drug + 35 days
- is completely missing an onset date and end date
- is completely missing an onset date and the end date is on or after the first dose of study drug and on or before the stop of study drug + 35 days.

REACH TRIAL

Stop of study drug is recorded in the End of Treatment form as the Date of Last Dose.

Missing start and stop dates for TEAEs will be handled as follows:

- ??-MMM-YYYY: If the AE month and year are different from the month and year of the first dose of study drug, assume 01-MMM-YYYY. If the month and year are the same as the first dose of study drug month and year and the AE end date (after any imputation) is on or after the first dose of study drug, then assume the date of the first dose of study drug. If the AE month and year are the same as the first dose of study drug month and year and the AE end date (after any imputation) is prior to the first dose of study drug, then assume the end date for the onset date.
- DD-???-YYYY/??-??-YYYY: If the AE year is different from the year of first dose of study drug, assume DD-JAN-YYYY/01-JAN-YYYY of the collected year. If the AE year is the same as the first dose of study drug year (and in the case of AEs that are non ongoing the AE end date (after any imputation)) is on or after the first dose of study drug, then assume the date of the first dose of study drug. If the year is the same as the first dose of study drug and the AE end date (after any imputation) is prior to the first dose of study drug, then assume the end date for the onset date.

Missing end dates:

- ??-MMM-YYYY: Assume the last day of the month
- DD-???-YYYY: Assume DD-DEC-YYYY
- ??-???-YYYY: Assume 31-DEC-YYYY.

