10.1.6 Treatment exposure and compliance

Exposure and study drug accountability (compliance) will be presented for patients in the Safety Analysis Set.

Study drug exposure

Descriptive statistics will be used to summarize duration of exposure both as a continuous measure in days and weeks and by category: < 8 weeks, \geq 8 weeks, \geq 16 weeks, \geq 24 weeks, \geq 36 weeks, \geq 48 weeks, average daily dose, and cumulative dose.

Study drug accountability

Descriptive statistics will be used to summarize compliance as a continuous measure, and by category: < 80%, 80-120%, \geq 120%. Drug accountability will be presented in a listing, presented by FSHD type, treatment, and patient. For each patient, first dose date, last dose date, and treatment duration will be presented; and at each time-point, for dispensed study drug: bottle number, date and study day tablets were dispensed, and number of tablets dispensed; for returned study drug: date returned, number of tablets returned. The following treatment compliance data will be presented: Number of tablets taken, number of tablets prescribed, duration, and compliance.

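### SAP 9.3.2.5 does not tie the visit-level compliance denominator to the dispensing interval; with the SAP's usual meaning of first and last dose, a fully adherent five-visit patient scores 20%

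*SAP*

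**What the plan says.** SAP 9.3.2.5 opens with the data source: "The following will be derived from data collected in the Study Drug Accountability form of the eCRF". Two blocks of derivations follow.

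- Visit block, headed "For each visit post baseline". The numerator is "Number of tablets taken = Number of tablets dispensed at previous visit – Number of tablets returned for the visit". The denominator is two tablets per day times a duration, with "Duration = (date of last dose) – (date of first dose) + 1".
- Whole-study block. It gives "Treatment Duration = (Date of last dose) – (Date of first dose) + 1", and for the overall compliance denominator "Total number of tablets prescribed = Sum of tablets prescribed over all visits".

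SAP 10.1.6 summarises compliance as a continuous measure and in three categories: below 80%, 80 to 120%, and 120% or more. For the accountability listing it states: "For each patient, first dose date, last dose date, and treatment duration will be presented". The items listed at each time point are bottle numbers, dispensing and return dates, and tablet counts. A separate duration item is listed with the compliance data.

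Two other sections show how the SAP normally uses the dates. SAP 9.3.1.3 makes the date of first dose Day 1. SAP 9.3.4.1 says: "Stop of study drug is recorded in the End of Treatment form as the Date of Last Dose".

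**The concern.** The visit-level numerator counts tablets over one dispensing interval, between 28 and 84 days on the planned schedule. The visit-level denominator carries no interval qualifier, and its formula matches the whole-study one. If both dates are the patient's own first and last dose, each interval's tablets are divided by the whole treatment period, and the overall denominator counts that period once per visit.

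Compliance is a formal output that a reader would consult when interpreting a small or null treatment effect. A definition that places the same perfectly adherent patient on either side of the 80% boundary, depending on how the programmer reads two dates, is not reproducible. On the literal reading the score also falls as more visits are counted, so early leavers would look more compliant than completers.

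**Working it through.** The documents state no compliance figure to reproduce, so the check applies the SAP 9.3.2.5 formulas to a fully adherent completer.

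Inputs:
- Treatment duration of 336 days: SAP 8.3.1 gives 335 as the planned duration minus 1.
- Two tablets per day: SAP 9.3.2.5.
- Five post-baseline visits, at Days 28, 84, 168, 252 and 336: schedule of assessments, SAP Appendix B.
- Assumptions: all unused tablets are returned, and visit-day doses come from the earlier supply.

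Tablets taken by interval: 2 x 28 = 56, 2 x 56 = 112, then 2 x 84 = 168 three times. Total 672.

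The two dates can be read in several ways:

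| Reading of first and last dose | Tablets prescribed, summed | Overall compliance | Category |
|---|---|---|---|
| Patient level, as elsewhere in the SAP | 5 x (2 x 336) = 3360 | 672/3360 = 20.0% | <80% |
| First dose of study to last dose before the visit | 56 + 168 + 336 + 504 + 672 = 1736 | 672/1736 = 38.7% | <80% |
| Within the interval, each visit day counted once | 672 | 672/672 = 100% | 80-120% |
| Within the interval, each intermediate visit day counted in both neighbours | 2 x (336 + 4) = 680 | 672/680 = 98.8% | 80-120% |

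On the patient-level reading, the five visit scores are 56/672 = 8.3%, 112/672 = 16.7%, and 168/672 = 25% three times.

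In general, that reading divides true adherence by k, the number of visits counted. A fully adherent patient scores 100%, 50%, 33.3%, 25% or 20% for k = 1 to 5. With five visits, reaching 80% would need 0.8 x 3360 = 2688 tablets, four times the number prescribed.

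A patient fully adherent until stopping drug on Day 100 has taken 200 tablets. The score is 200/(3 x 200) = 33.3% if three visits are counted. It is 200/(5 x 200) = 20% if the patient stays in follow-up and all five are counted. Protocol 4.3.2 encourages patients who stop drug to remain in the study, so this case can arise.

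**The case against.** The best defence is that an interval was plainly meant. The formula sits under a per-visit heading and its numerator is an interval count. Summing prescribed tablets over visits makes sense only for intervals. The section uses two labels, Duration and Treatment Duration, and the SAP 10.1.6 listing also shows them separately. The accountability form is the named source, and it may hold interval dose dates; Protocol 5.7 adds that diaries may be used. The End of Treatment form is cited for defining adverse events, not compliance.

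This stands as evidence of intent, and a careful programmer would probably choose the interval reading. It does not repair the rule. The two labels carry identical formulas, and the accountability-form sentence introduces both blocks, so it does not separate them. The listing shows no interval dose dates. The form and the table shells are outside the documents and might settle the matter, but that cannot be assumed.

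Stronger inferences should be resisted:
- A reader might infer that the sponsor has chosen a whole-study denominator at each visit. The contextual evidence points the other way.
- A reader might infer that the trial has no usable adherence measure. Average daily dose uses neither tablets prescribed nor the visit-level duration; for the completer above it is 672 x 15/336 = 30 mg/day.
- A reader might infer that adherent and non-adherent patients cannot be told apart. Among patients with equal visit counts the ranking survives: with five visits, half adherence scores 336/3360 = 10% against 20%. The scale, the categories and comparisons across different visit counts are what fail.
- The double-counted visit days matter little: 98.8% against 100%, with no category crossed.

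**Conclusion.** The concern holds as a defect in a written derivation. Applied with the SAP's usual patient-level meaning of first and last dose, SAP 9.3.2.5 gives a fully adherent five-visit completer 20% and the <80% category, and 100/k % for k visits counted. The probable intention gives 98.8 to 100%, but the text does not say so.

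The figures assume the planned visit days and complete tablet returns. The 20% applies only when five visits are counted.

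The reach is narrow: the compliance summary and listing in SAP 10.1.6. Cumulative dose and average daily dose do not use tablets prescribed. No analysis set is defined by compliance and no efficacy analysis uses it, so the documents do not support any inference that the primary result is at risk.

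**What to change.** Two changes to SAP 9.3.2.5:

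1. Set the total number of tablets prescribed to 2 x Treatment Duration, in place of the sum over visits. The completer then scores 672/672 = 100% however the visit-level dates are read.
2. Define visit-level duration as the days in that dispensing interval: from the previous dispensing date to the day before the current visit, or to the date of last dose if that is earlier. The final interval on drug includes the day of last dose, so that intervals do not overlap and they sum to Treatment Duration.

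Check on the planned schedule: 27 + 56 + 84 + 84 + 85 = 336 days, or 672 tablets. For the patient stopping on Day 100: 27 + 56 + 17 = 100 days, or 200 tablets. If visit-day doses come from the earlier bottle, the completer's first visit reads 56/54 = 103.7% and the last 168/170 = 98.8%. Both stay within 80 to 120%, and the overall figure is unaffected.

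The cost is two lines of SAP text and the matching programming, using dispensing and dose dates that the 10.1.6 listing already shows. There is one small downside. Protocol 4.3.2 allows study drug to be restarted after discontinuation, and any off-drug gap would count as non-compliance in the overall figure, as it already does in average daily dose. The SAP should say so.

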5.1.2. Treatments Administered

Study drug tablets (losmapimod or placebo) will be dispensed to patients at the visits detailed in [Table 7](#).

During the 48-week placebo-controlled treatment period, patients will receive 15 mg losmapimod PO BID or placebo BID with food.

If a patient misses a dose and it is more than 6 hours until the next planned dose, the patient will be instructed to take the missed dose and resume study drug dosing as normal. If it is less than 6 hours until the next planned dose, the patient will be instructed to skip the missed dose and then resume study drug dosing as normal.

On visit days during which blood collection will occur for PK assessment (see [Table 7](#)), patients should wait to take their dose in the clinic.

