5.4.2. Study Drug Accountability

During the study, each patient will be provided a sufficient quantity of study drug to allow for dosing until their next scheduled visit plus additional tablets to cover the visit window. If needed, patients may be provided additional study drug via a courier service, as applicable. At the next scheduled clinic visit, patients must return their bottles of study drug for accountability.

The Investigator will maintain accurate records of receipt of all study drug, including dates of receipt. In addition, accurate records will be kept regarding when and how much study drug is dispensed and used by each patient in the study. Reasons for departure from the expected dispensing regimen must also be recorded. At the completion of the study, to satisfy regulatory

requirements regarding drug accountability, all study drug will be reconciled and retained or destroyed according to applicable regulations.

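### Counting a missing tablet return as zero returned credits every dispensed tablet as taken and biases the compliance and dose-exposure tables upward

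*SAP*

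**What the plan says.** SAP 9.3.2.5 builds compliance from two quantities. The numerator is "Number of tablets taken = Number of tablets dispensed at previous visit – Number of tablets returned for the visit". The denominator is "Tablets Prescribed = Duration x 2", where duration runs from first to last dose, inclusive. Overall compliance is the ratio of the two sums over visits. The same numerator feeds the dose summaries: "Cumulative dose is the total number of tablets taken across all study days times 15 mg", and average daily dose is that figure divided by treatment duration.

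For a missing return count, "the Number of tablets returned will be assumed to be 0 in the calculations of treatment exposure and compliance". Only the patient listings keep the count as missing. The section sets no upper limit on the result.

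Protocol 5.1.2 gives the regimen: "patients will receive 15 mg losmapimod PO BID or placebo BID with food". With the 15 mg tablets of Protocol 5.3, this is two tablets a day. Protocol 5.4.2 says each supply must allow "dosing until their next scheduled visit plus additional tablets to cover the visit window", and 5.4.1 says the same in similar words. Protocol 5.4.2 also requires bottles to be brought back at the next clinic visit.

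SAP 10.1.6 presents compliance and exposure on the safety analysis set. Compliance is shown as a continuous measure and in three categories: below 80%, 80–120%, and 120% or more.

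**The concern.** A missing return count carries no information on how many tablets were swallowed. Replacing it with zero is not a neutral choice: returns cannot be negative, so zero gives the largest possible number taken. Because the bottle normally holds more than the patient needs up to the next visit, the imputed numerator will usually exceed the denominator for that interval.

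The SAP is more careful elsewhere. In SAP 10.2.2.1 a missing PGIC counts as not improved or as worsened. In SAP 10.2.1.2 a missing RSA change counts as below the meaningful score difference. In SAP 9.3.3.2 missing dynamometry stays missing. For compliance the missing value goes to the favourable extreme, and neither a sensitivity summary nor a count of imputed intervals is planned.

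At stake is how reliably the compliance and exposure tables describe intake. The error can also run the other way in appearance: an early stopper who keeps the bottle may look as if they had taken far more than prescribed.

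**Working it through.** The documents state no compliance figure to reproduce, so the SAP formulas are applied directly.

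**Inputs**
- Two 15 mg tablets a day (Protocol 5.1.2 and 5.3), so 30 mg planned per day.
- Visits at Weeks 4, 12, 24, 36 and 48 (schedule of assessments), giving intervals d of 28, 56, 84, 84 and 84 days, 336 in total.
- Visit window of ±7 days (SAP 9.5.1).
- Surplus s per dispensing: not stated. Assumed to be 7 days (14 tablets), with 0 and 14 days as the range.

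**One interval without a count, visit on schedule**

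Compliance = 100 × 2(d + s) / (2d). With s = 7:
- 4 weeks: 35/28 = 125.0%
- 8 weeks: 63/56 = 112.5%
- 12 weeks: 91/84 = 108.3%

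**No counts at any visit**

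Overall = 100 × (336 + 5s) / 336.

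| Surplus | Overall compliance | Cumulative dose | Average daily dose |
|---|---|---|---|
| 0 days | 336/336 = 100.0% | 672 × 15 = 10,080 mg | 30.0 mg |
| 7 days | 371/336 = 110.4% | 742 × 15 = 11,130 mg | 33.1 mg |
| 14 days | 406/336 = 120.8% | 812 × 15 = 12,180 mg | 36.25 mg |

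These values do not depend on actual intake, provided first and last dose dates span the period. With 7 days of surplus the patient falls in the 80–120% category.

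**Visit timing, s = 7**
- Seven days early: 35/21 = 166.7%, 63/49 = 128.6%, 91/77 = 118.2%.
- Seven days late: exactly 100% in every interval.

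**One missing count, true intake a in the other intervals, s = 7**

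Overall = 100 × [a(336 − d) + d + 7] / 336.
- a = 1.0: 343/336 = 102.1%, whichever count is missing.
- a = 0.7: 250.6/336 = 74.6% (4-week count missing) to 267.4/336 = 79.6% (12-week count missing).
- a = 0.5: 189/336 = 56.25% to 217/336 = 64.6%.

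**Early stop, s = 7**

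The patient takes every dose to Week 12 with counts available, stops 14 days after the Week 12 dispensing and never returns the bottle. The zero-return rule is assumed to be applied to that dispensing.
- Dispensed at Week 12: 2 × (84 + 7) = 182. Prescribed: 2 × 14 = 28. Interval compliance: 182/28 = 650%.
- Overall: (56 + 112 + 182) / (2 × 98) = 350/196 = 178.6%.
- Average daily dose: 350 × 15 / 98 = 5,250/98 = 53.6 mg, against 30 mg planned.

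**The case against.** The strongest reply is that little depends on this. Compliance enters no analysis set, estimand, primary model or sensitivity analysis, and on-treatment status and exposure duration come from dates. Bottles must be returned, tablet counts are scheduled at every post-baseline clinic visit through Week 48 and at early termination, and drug is reconciled at study end, so missing counts may be few. The rule is prespecified, the listings show the missing value, and plasma losmapimod at Weeks 4 and 48 gives a check on intake that needs no count. All of this stands as a limit on importance. None of it corrects the summary tables, which will carry the imputed values without marking them.

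Three stronger readings are tempting, and the documents do not support them.

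- *Patients without a count are always recorded above 100%.* With no surplus, or with a 7-day surplus and a visit on the last day of the window, the interval value is exactly 100%. Overall compliance can stay well below 100% when the other counts show poor intake. What follows from the documents is upward bias.
- *A patient who took nothing would show 108% or more.* Duration runs from first to last dose, so an interval with no doses has no defined denominator when calculated by visit. A patient who was never dosed is outside the safety analysis set on which compliance is presented.
- *Patients who fail to return bottles are the poor adherers.* Neither document says so, and a count may be missing because the site did not record it. The point does not need this premise: an unknown count is no evidence of full intake.

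**Conclusion.** The point holds as an upward bias in descriptive tables, and it is minor. The direction follows from the documents alone: zero is the lowest possible return count, so tablets taken, compliance, cumulative dose and average daily dose are set at their maximum for the affected interval.

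The size rests on the unstated surplus. Across assumed surpluses of 0 to 14 days, overall compliance with no counts at all runs from 100.0% to 120.8%. A single missing count moves the patient's figure much less. The early-stopper case is the most distorting because the denominator ends at the last dose while the numerator keeps the whole bottle. How many counts will be missing is unknown, so the effect on group summaries cannot be estimated.

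A reader might infer that the efficacy result or the safety population is compromised. It is not: the FAS, the safety set, treatment duration and the primary MMRM do not use tablet counts.

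**What to change.** Replace the imputation sentence in SAP 9.3.2.5 with a rule along these lines:

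1. If the return count is missing, tablets taken and compliance for that interval are missing.
2. Overall compliance is computed over intervals with a count, dropping the others from both numerator and denominator. A patient with no counts is not evaluable for compliance.
3. The number of intervals without a count is reported by treatment group.
4. If cumulative or average daily dose needs a value, tablets taken for that interval are capped at the number prescribed, and the result is labelled an upper bound.

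In the early-stop example, overall compliance becomes 168/168 = 100% on the counted intervals. The capped cumulative dose is (168 + 28) × 15 = 2,940 mg, or 2,940/98 = 30 mg a day.

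The cost is a short SAP edit, and a table shell may need an extra row. No new data are required. Some patients will have no evaluable compliance. The remaining figure can still be optimistic if intake was lower in the uncounted intervals, and the cap still credits full intake, which is why it needs its label.

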9.3.3 Efficacy derivations

9.3.3.1 Primary endpoint

Change from baseline in average total RSA Q1-Q5 with 500 g wrist weight at Week 48, where the average is applied over both arms.

The RWS (total RSA Q1-Q5) measurements required for the analysis of the primary endpoint are those assessed at baseline and at weeks 4, 12, 24, 36 and 48, on both the dominant and non-dominant arms. At each visit the RWS for each arm (Left and Right) is the sum of the 5 RSA measurements: Q1+Q2+Q3+Q4+Q5, where the weight used is 500g. The average total RSA is the average of the two totals:

Average = Mean of (Total for Left Arm with 500g weight, Total for Right Arm with 500g weight)

Change from baseline is derived as specified in 9.2. above.

Note: the average over both arms per visit needs to be calculated before computing changes from baseline.

If an arm is not tested for RWS, and the reason code is W='Weakness related', then the RWS for that arm should be imputed as 0.

Because the RWS data are used in the primary endpoint analysis for this study, Fulcrum or its designated vendor will perform additional cleaning of these data. Fulcrum or its designated vendor will use the following criterion to identify potentially invalid data points: post-baseline data points that show a change (increase or decrease) >50% from the previous result on total RSA Q1-Q5. Records meeting this criterion will be sent to the RWS vendor for further investigation. After blind review, the RWS vendor will communicate to Fulcrum or its designated vendor any records that are deemed invalid because of problems with the software and should therefore not be included in the analysis. These rare sessions, if any, will be flagged by the RWS vendor, and their associated results, including total RSA Q1-Q5, total RSA Q1-Q4, sum of Q1 and Q3, and all 5 individual quadrants, will be removed from the RWS analysis (also see 9.3.3.3).

